### **Important notes for the accurate assessment of temperature:**

Subjects are to measure body temperature once per day (in degrees Celsius), preferably always at the same time. The optimal time for measurement is the evening, when body temperature is highest. Temperature is also to be measured at the time of any apparent fever. The highest observed daily temperature and the route of measurement are to be recorded in the diary card, and the highest temperature will be recorded by the site in the CRB. The preferred route for this study is oral. Pre-vaccination temperature is also systematically collected by the investigator on the source document. Tympanic and temporal artery thermometers must not be used.

#### **2.1.4.1.2.3 Unsolicited Adverse Events**

In addition to recording solicited reactions, subjects will be instructed to record any other medical events that may occur during the 28-day period after vaccination. Space will be provided in the diary card for this purpose.

Information on SAEs will be collected and assessed throughout the study, from inclusion until 28 (+ 7) days after vaccination. Any SAE occurring at any time during the study will be reported by the Investigator in the CRB according to the completion instructions provided by the Sponsor; this includes checking the “Serious” box on the AE CRF and completing the appropriate Death/Safety Complementary Information CRFs. All information concerning the SAE is to be reported either as part of the initial reporting or during follow-up reporting if relevant information became available later (e.g., outcome, medical history, results of investigations, copy of hospitalization reports). See Section 10 of the protocol for further details on SAE reporting.

For each unsolicited AE (whether serious or non-serious), the following information is to be recorded:

- Start and stop dates
- Intensity of the event

For measurable unsolicited AEs that are part of the list of solicited reactions, the size of the AE as well as the temperature for fever will be collected and analyzed based on the corresponding scale used for solicited reactions (see [Table 2](#) and [Table 3](#)).

All other unsolicited AEs will be classified according to the following intensity scale:

- Grade 1: A type of AE that is usually transient and may require only minimal treatment or therapeutic intervention. The event does not generally interfere with usual activities of daily living.

---

 The stop date of all related AEs will be actively solicited. For other events, the investigator will provide the stop date when it becomes available. AEs for which no stop date was obtained during the course of the study will be considered as ongoing at the end of the study.

- Grade 2: A type of AE that is usually alleviated with additional therapeutic intervention. The event interferes with usual activities of daily living, causing discomfort but poses no significant or permanent risk of harm to the research participant.
- Grade 3: A type of AE that interrupts usual activities of daily living, or significantly affects clinical status, or may require intensive therapeutic intervention.
- Whether the AE was related to the investigational product (for unsolicited systemic AEs)
- The Investigator will assess the causal relationship between the AE and the investigational product as either "Not related" or "Related", as described in Section 9.1.3.5 of the protocol.
- Action taken for each event (e.g., medication)

The action(s) taken by the subject to treat and/or manage any unsolicited AEs will be classified in the CRB using the following list (all applicable items should be checked):

- None
- Medication
- Health care provider contact
- Hospitalized
- Whether the AE was serious

For each SAE, the investigator will complete all seriousness criteria that apply (outcome and elapsed time)

- Whether the AE was AESI
- Whether the AE caused study discontinuation

#### 2.1.4.1.2.4 Adverse Events of Special Interest

AESIs will have the same detailed information collected as SAEs (collected throughout the study). These include (1):

- new onset of Guillain-Barré syndrome
- encephalitis/myelitis (including transverse myelitis)
- Bell's palsy
- optic neuritis
- brachial neuritis

#### 2.1.4.1.2.5 Assessment of Causality

The Investigator will assess the causal relationship between each unsolicited systemic AE and the product administered as either not related or related, based on the following definitions:

Not related – The AE is clearly/most probably caused by other etiologies such as subject’s underlying condition, therapeutic intervention, or concomitant therapy; or the delay between vaccination and the onset of the AE is incompatible with a causal relationship; or the AE started before the vaccination (screening phase, if applicable).

Related – There is a “reasonable possibility” that the AE was caused by the product administered, meaning that there is evidence or arguments to suggest a causal relationship.

Note: By convention, all injection site AEs (solicited and unsolicited) and all solicited systemic reactions are considered to be related to the administered product and therefore are referred to as reactions and do not require the Investigator’s opinion on relatedness.

AEs likely to be related to the product, whether serious or not, that persist at the end of the study will be followed up by the Investigator until their complete disappearance or the stabilization of the subject’s condition. The Investigator will inform the Sponsor of the date of final disappearance of the event or the date of “chronicity” establishment.

#### **2.1.4.2 Laboratory safety variables**

No laboratory safety data will be obtained in the study.

#### **2.1.4.3 Vital signs variables**

No vital sign data will be obtained in the study.

#### **2.1.4.4 Electrocardiogram variables**

No electrocardiogram data will be obtained in the study.

#### **2.1.5 Immunogenicity endpoints**

The endpoints for the evaluation of immunogenicity are:

- GMT of HAI at D0 and D28
- Individual Geometric Mean Titer Ratio (GMTR) of HAI at D28/D0
- Seroconversion rate (percentage of subjects with HAI titer <10 [1/dil] at D0 and post-injection titer  $\geq$ 40 [1/dil] at D28, or HAI titer  $\geq$ 10 [1/dil] at D0 and a  $\geq$ 4-fold increase in HAI titer [1/dil] at D28)

---

 ICH Guidelines, Clinical Safety Data Management E2A

- Seroprotection rate (percentage of subjects with HAI titer  $\geq 40$  [1/dil]) at D0 and D28

### **Anti-Influenza Virus Antibody Titration by Inhibition of Hemagglutination**

Assays will be performed by the Sanofi Pasteur laboratory (GCI, Swiftwater, PA, USA) or at an external testing laboratory under GCI responsibility. The address is provided in the sample handling procedures.

Test serum samples and quality control sera (sheep, ferret, and/or human sera) are incubated with Sigma Type III neuraminidase from *Vibrio cholerae* to eliminate non-specific inhibitors. Adsorption of spontaneous anti-species agglutinins is then performed by incubating the test serum samples and quality control sera with a red blood cell (RBC) suspension. Following this, the mixtures are centrifuged and the supernatants containing the treated test sera are collected for testing. Ten two-fold dilutions (starting at 1:10) of the treated test serum samples and quality control sera are incubated with a previously titrated influenza antigen at a concentration of 4 hemagglutination unit (HAU)/25  $\mu$ L. Influenza antigen is not added to the serum control wells containing only serum and RBCs. The mixture is then incubated and a RBC suspension is added. Following incubation, the results are read. The endpoint of the assay is the highest serum dilution in which complete inhibition of hemagglutination occurred. Each serum sample is titrated in two independent assay runs, and the 2 values, which cannot differ by more than 1 two-fold dilution, are reported. The HAI GMT between the 2 values is calculated at the time of statistical analysis. The lower limit of quantitation (LLOQ) is set at the lowest dilution used in the assay, 1:10. If the first/lowest serum dilution exhibits hemagglutination, the serum antibody titer is reported as  $<10$  (1/dil). If the last/highest serum dilution exhibits complete inhibition of hemagglutination, the serum antibody titer is reported as  $\geq 10$  240 (1/dil).

In this study, QIV-HD will be compared to a local QIV-SD, and it is possible that the two vaccines contain different strains based on comparison of strains between Sanofi Pasteur QIV-HD (based on WHO / VRBPAC recommendations) and a local QIV-SD (based on NIID). Sanofi Pasteur plans on performing the HAI testing using both the QIV-HD and QIV-SD strains as test antigens for all the subjects, irrespective of the vaccine received. For example, if QIV-HD is comprised of a, b, c and d strains and QIV-SD is comprised of a, b, c and “d-like” strains (3 common and 1 “-like strain”), the proposed testing strategy would require HAI testing of sera from all subjects (irrespective of the vaccine received) with a, b, c, d and “d-like” strain test antigens in order to evaluate the comparability between the “-like strains” in this study.

## **2.2 DISPOSITION OF PATIENTS**

This section describes patient disposition for both patient study status and the patient analysis populations.

Enrolled subjects are defined as subjects who signed the informed consent and met the inclusion criteria and did not meet any of the exclusion criteria, i.e., CRB have been created for them.

Randomized subjects consist of all enrolled subjects who have a vaccine dose number allocated and recorded in the IRT database, regardless of whether the vaccine dose kit was used.

Duration of the study in each cohort and the summary of inclusion and exclusion criteria by randomized groups will be presented using a summary table.

Randomized subjects will be summarized by sites and vaccine groups for each cohort.

For subjects' study status, the total number of subjects in each of the following categories will be presented in the clinical study report using a flowchart diagram or summary table:

- Enrolled subjects
- Randomized subjects
- Randomized and not vaccinated subjects
- Randomized and vaccinated subjects
- Subjects who did not complete the study
- Subjects who completed the study

For all categories of subjects (except for the enrolled category), percentages will be calculated using the number of randomized subjects as the denominator. Reasons for study discontinuation will be supplied in tables giving numbers and percentages by study groups.

The subjects who discontinued the study and subjects who completed the study will be listed separately. The subjects with at least one inclusion criterion not met or at least one exclusion criterion met will also be listed.

Randomization strata, vaccine allocation, vaccine administration, and adherence to schedule will be summarized in tables giving numbers and percentages by study groups on randomized subjects. Subjects randomized in a group but who received an unallocated study vaccine will be listed.

All critical or major deviations potentially impacting immunogenicity analyses, randomization and drug-dispensing irregularities, and other major or critical deviations will be summarized in tables giving numbers and percentages of deviations by study groups.

Additionally, the analysis sets for safety and immunogenicity will be summarized in a table by number of subjects on the randomized subjects.

- Safety analysis set (SafAS)
- Immunogenicity analysis set: full analysis set (FAS) /per-protocol analysis set (PPAS)

Subjects (observations) excluded from the immunogenicity analyses will be listed.

### **2.2.1 Randomization and drug dispensing irregularities**

Randomization and drug-dispensing irregularities occur whenever:

1. A randomization is not in accordance with the protocol-defined randomization method, such as a) an ineligible subject is randomized, b) a subject is randomized based on an incorrect stratum, c) a subject is randomized twice, or d) in a dynamic randomization

scheme the treatment assignment is, in fact, not random, due to a computer program error.

OR

2. A subject is dispensed an IMP kit not allocated by the protocol-defined randomization, such as a) a subject at any time in the study is dispensed a different treatment kit than as randomized (which may or may not contain the correct-as-randomized IMP), or b) a nonrandomized subject is treated with IMP reserved for randomized subject.

Randomization and drug-dispensing irregularities will be monitored throughout the study and reviewed on an ongoing basis.

All randomization and drug-dispensing irregularities will be documented in the clinical study report. If the number of irregularities is large enough to make a tabular summary useful, the irregularities will be categorized and summarized among randomized subjects (number and percentages). Nonrandomized, treated patients will be described separately.

Randomization and drug-dispensing irregularities to be prospectively identified include but are not limited to:

Randomization and drug allocation irregularities
IMP administered but not as per protocol
IMP given outside Randomization procedure
IMP intake is prior to Randomization
Randomization procedure not performed in the correct sequence as specified in the protocol
Subject randomized twice
IMP number actually administered to the subject is different from the IMP number allocated according to the Randomization list
Same kit number used for several subjects
Wrong stratum of randomization
Kit not available
Randomization by error
Subject switched to another site

### 2.3 ANALYSIS SETS

Subjects vaccinated without being randomized will not be considered randomized and will not be included in any analysis sets performing immunogenicity analyses.

The randomized subject includes any subject who has been allocated to a randomized treatment regardless of whether the treatment kit was used.

For any subjects randomized more than once, only the data associated with the first randomization will be used in any analysis set. The safety experience associated with any later randomization will be assessed separately.

### **2.3.1 Full analysis set**

The full analysis set (FAS) will include all randomized subjects who received the study vaccine and had a post-vaccination blood sample HAI result for at least one strain. Subjects will be analyzed according to the vaccine group to which they were randomized.

### **2.3.2 Per-protocol analysis set**

The per-protocol analysis set (PPAS) is a subset of the FAS. The subjects presenting with at least one of the following relevant protocol deviations will be excluded from PPAS.

- Subject did not meet all protocol-specified inclusion criteria or met at least one of the protocol-specific exclusion criteria
- Subject did not receive vaccine
- Subject received a vaccine other than the one that he/she was randomized to receive
- Preparation and/or administration of vaccine was not done as per-protocol
- Subject did not provide the post-dose serology sample at V3 in the proper time window (i.e., 28 to 35 days after vaccination) or a post-dose serology sample (V3) was not drawn
- Subject received a protocol-restricted therapy / medication / vaccine (prohibited therapies / medications / vaccines should have been indicated in Section 6.7 of the protocol).

In addition to the criteria listed above, subjects will also be excluded from the PPAS if their HAI serology sample at V3 did not produce a valid test result for all strains.

The PPAS definition will be finalized before the database lock.

### **2.3.3 Safety analysis set**

The safety analysis set (SafAS) is defined as those subjects who have received the study vaccine. All subjects will have their safety analyzed according to the vaccine they actually received.

Safety data recorded for a vaccine received out of the protocol design will be excluded from the analysis (and listed separately).

---

 For which safety data are scheduled to be collected

## **2.4 STATISTICAL METHODS**

### **2.4.1 Demographics and baseline characteristics**

Continuous data will be summarized using the number of available data, mean, standard deviation (SD), median, minimum and maximum for each vaccine group. Categorical and ordinal data will be summarized using the number and percentage of subjects in each vaccine group.

Parameters will be summarized on the safety analysis set analyzed in the vaccine group to which they were randomized. Demographic characteristics will also be summarized on the randomized subjects, full analysis set and per-protocol analysis set for each vaccine group.

Parameters described in [Section 2.1.1](#) will be summarized by vaccine group and overall using descriptive statistics.

No specific description of the safety parameters will be provided at baseline. If relevant, the baseline values will be described along with each safety analysis.

No specific description of the immunogenicity parameters will be provided at baseline. If relevant, the baseline values will be described along with each immunogenicity analysis.

In addition, demographic data will also be presented in the listings.

### **2.4.2 Prior or concomitant medications**

Reportable medications will be presented for the safety analysis set by vaccine groups. Reportable medications will be also summarized by category and the presence of prophylactic medication.

### **2.4.3 Analyses of efficacy endpoints**

Not applicable

### **2.4.4 Analyses of safety data**

The summary of safety results will be presented by vaccine groups. The safety data in Cohort 1 will be summarized and reviewed by the Sponsor at a planned Safety Management Team meeting as Early Safety Data Review.

#### ***General common rules***

All safety analyses will be performed in Cohort 2 and all subjects, combining both Cohort 1 and Cohort 2 (hereafter, Cohort 1+Cohort 2), for the SafAS defined in [Section 2.3.3](#), unless otherwise specified, using the following common rules:

- Safety data from subjects who do not belong to the safety analysis set will be listed separately

- The analysis of the safety variables will be essentially descriptive and no systematic testing is planned. The main parameters will be described using the number and percentage of subjects with 95% CIs (Clopper-Pearson method) (2) in each vaccine group.

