1.3.2 Potential Risks to Subjects

As with any vaccine, it is important to note that vaccination with QIV-HD may not protect all recipients against the disease it is designed to prevent (i.e., influenza). See below for other potential risks.

Possible Reactions to Blood Draw

Venipuncture causes transient discomfort and may cause temporary hypotension from a vasovagal response (e.g., fainting). If pressure is not applied long enough to the venipuncture site, bruising due to bleeding beneath the skin may occur. Infection at the site of needle insertion could theoretically occur but is exceedingly rare when the standard sterile technique is utilized.

Possible Reactions to Vaccination

Vaccine injection into the deltoid muscle causes transient discomfort. Immediate and potentially life-threatening allergic reactions to the vaccine could be manifested by adverse events (AEs) such as laryngeal edema, asthma, or hypotension. These types of reactions are exceedingly rare and would most likely occur in persons with a severe reaction to influenza vaccine in the past.

The rate of injection site reactions is expected to be higher with the SC route compared to the IM route due to the fact that the inflammatory reactions induced by the vaccines are closer to the surface of the skin and therefore more visible to direct examination.

Post-marketing Experience with QIV-SD (Fluzone Quadrivalent), TIV-HD (Fluzone High-Dose) and TIV-SD (Fluzone)

There is no post-marketing experience for QIV-HD as it has not been licensed yet.

Post-marketing experience with QIV-SD and TIV-HD has not identified any events other than those described below, which were spontaneously reported during the post-approval use of TIV-SD, for addition to the QIV-SD package insert (11).

The following events have been spontaneously reported during the post-approval use of TIV-SD and TIV-HD (12). These events are reported voluntarily from a population of uncertain size, consequently it is not always possible to reliably estimate the frequency of the events or establish a causal relationship to vaccine exposure. AEs were included based on one or more of the following factors: severity, frequency of reporting, or strength of evidence for a causal relationship to TIV-SD:

- *Blood and Lymphatic System Disorders:* thrombocytopenia, lymphadenopathy
- *Immune System Disorders:* anaphylaxis, other allergic/hypersensitivity reactions (including urticaria, angioedema)

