2 STUDY OBJECTIVES

Safety

To describe the safety profile of subjects in each group.

Immunogenicity

To describe the immune responses induced by each group (as assessed by HAI GMTs and seroconversion rates) for the 4 common virus strains at 28 days post-vaccination.

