5.1.2 Justification of the Study Design

The objectives of QHD00008-DFI15130 will be to assess the safety and immunogenicity (as assessed by HAI GMTs and seroconversion rates at 28 days post-vaccination) of QIV-HD when administered SC and IM compared with the local QIV-SD.

The control product is the local QIV-SD because it is the only seasonal influenza vaccine licensed in Japan.

In addition, the route of administration of seasonal influenza vaccine is SC in Japan, whereas IM in the US and Canada. Therefore, the QIV-HD will be administered by SC or IM method in this study.

The investigational QIV-HD has never been administered to Japanese subjects. However, given the acceptable safety data generated from the millions of doses of TIV-HD administered in the US and Canada and the fact that no changes will be made to the drug substance manufacturing process of QIV-HD compared to the TIV-HD process currently licensed in the US and Canada, the Sponsor considers that the risk/benefit ratio is appropriate for the conduct of a Phase I/II clinical study with QIV-HD with a small group included for an early safety data review.

Given the different volumes and administration routes of the QIV-HD and the local QIV-SD vaccines, QHD00008-DFI15130 will be a modified double-blind study in which only a designated administrator at each study site will know which vaccine has been administered to the subjects. The subjects and the Investigator/Sub-investigator in charge of the safety assessment will be blinded in order to decrease the potential bias in safety assessment.

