12.1.1 Hypotheses and Statistical Methods for Objectives

12.1.1.1 Hypotheses

Safety

No hypotheses are to be tested.

Immunogenicity

No hypotheses are to be tested.

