12.1.1.2 Statistical Methods

Safety

Safety results will be described for subjects in safety analysis set who received QIV-HD IM, QIV-HD SC, or QIV-SD SC. Solicited reactions (solicited injection site and systemic reactions), unsolicited AEs, SAEs, and AESIs will be summarized. The main parameters will be described with 95 % CI based on the Clopper-Pearson method (14).

- Unsolicited systemic AEs occurring within 30 minutes of injection (immediate unsolicited AEs)
- Solicited injection site reactions (pain, erythema, swelling, induration, and bruising) occurring within 7 days after the day of injection (D0 to D7) according to presence, time to onset, number of days of occurrence, maximum intensity (Grade 1, Grade 2, or Grade 3) and action taken. When more than 1 intensity level is reported within a time period, the highest intensity will be used.
- Solicited systemic reactions (fever, headache, malaise, myalgia, and shivering) occurring within 7 days after the day of injection (D0 to D7) according to presence, time to onset, number of days of occurrence, maximum intensity (Grade 1, Grade 2, or Grade 3) and

action taken. When more than 1 intensity level is reported within a time period, the highest intensity will be used.

- Unsolicited AEs occurring within 28 days after the day of injection by system organ class (SOC) and PT, time to onset, duration, maximum intensity (Grade 1, Grade 2, and Grade 3), and relationship to vaccination (for systemic AEs only).
- All SAEs that occur throughout the study by SOC and PT, time to onset, seriousness criteria, outcome and relationship to vaccination.
- All AESIs reported throughout the study by SOC and PT and relationship to vaccination.

Immunogenicity

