### 2.5.8.4 Confidence interval of the difference in proportions

The 2-sided 95% CI of the difference in proportions will be computed using the Wilson Score method without continuity correction, quoted by Newcombe (3) as follows:

Let  $\hat{\theta} = \pi_A - \pi_B$ , then if  $L = \hat{\theta} - \delta$  and  $U = \hat{\theta} + \varepsilon$  are respectively the lower and the upper limits of the CI, where:

$$\delta = Z_{0.025} \sqrt{\left\{ \frac{l_1(1-l_1)}{n_1} + \frac{u_2(1-u_2)}{n_2} \right\}}$$

$$\varepsilon = Z_{0.025} \sqrt{\left\{ \frac{l_2(1-l_2)}{n_2} + \frac{u_1(1-u_1)}{n_1} \right\}},$$

$l_1$  and  $u_1$  are calculated from the CI of the single proportion in group A given by:

$$\frac{\left( 2n_1 p_A + Z_{0.025}^2 \pm Z_{0.025} \sqrt{\left( Z_{0.025}^2 + 4n_1 p_A (1 - p_A) \right)} \right)}{2(n_1 + Z_{0.025}^2)},$$

$l_2$  and  $u_2$  are calculated from the CI of the single proportion in group B given by:

$$\frac{\left( 2n_2 p_B + Z_{0.025}^2 \pm Z_{0.025} \sqrt{\left( Z_{0.025}^2 + 4n_2 p_B (1 - p_B) \right)} \right)}{2(n_2 + Z_{0.025}^2)},$$

where  $Z_{0.025}$  is the upper 97.5th percentile of the standard normal distribution.

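### Protocol 1.4 and 5.1.2 pose a safety comparison of QIV-HD with QIV-SD, but no between-group estimate with an interval is planned for any reaction

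*SAP*

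**What the plan says.** The formal safety objective, in the Protocol Synopsis, Protocol section 2 and SAP 1.2, is descriptive: "To describe the safety profile of subjects in each group". Protocol 12.1.1.1 states for both safety and immunogenicity: "No hypotheses are to be tested".

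The Rationale (Protocol 1.4) and Design Justification (5.1.2) are worded differently. They give the objectives as assessing safety and immunogenicity "of QIV-HD when administered SC and IM compared with the local QIV-SD". On route, Protocol 1.3.2 adds an expectation: "The rate of injection site reactions is expected to be higher with the SC route compared to the IM route".

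The safety analysis follows the descriptive wording. Protocol 12.1.1.2: "The main parameters will be described with 95 % CI based on the Clopper-Pearson method". SAP 2.4.4, General common rules: "The analysis of the safety variables will be essentially descriptive and no systematic testing is planned", followed by "The main parameters will be described using the number and percentage of subjects with 95% CIs (Clopper-Pearson method", applied within each vaccine group. Nothing in Protocol 12.1.1.2 or SAP 2.4.4 specifies a difference, a ratio or a between-group interval for a safety endpoint.

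Immunogenicity is handled differently. Protocol 12.1.1.2 and SAP 2.4.5 specify GMT ratios and seroconversion differences with 95% CIs for each QIV-HD group against QIV-SD, and SAP 2.4.5 adds QIV-HD IM against QIV-HD SC. The method is in SAP 2.5.8.4: "The 2-sided 95% CI of the difference in proportions will be computed using the Wilson Score method without continuity correction".

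**The concern.** The trial randomises two routes and a control, and blinds subjects and safety assessors to limit bias in safety assessment. The planned safety output contains no estimate that uses the randomised contrast. Anyone asking how QIV-HD compares with QIV-SD on reactions, which is how Protocol 1.4 and 5.1.2 put the question, will have two separate intervals to look at.

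Two 95% intervals can overlap while the interval for their difference excludes zero. A reader who compares the intervals by eye may therefore report no difference when the data show an excess of reactions. A reader who computes the difference will do so after the fact, with their own choice of endpoints and method. The descriptive nature of the study does not explain the gap, because immunogenicity is just as descriptive and has the contrasts.

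**Working it through.** **Plan's own figure.** There is none to reproduce. The documents give no expected reaction rate, power, alpha or margin for safety. The planned numbers add up: 2 × 5 + 3 × 55 = 175, with 55 per arm in Cohort 2 (SAP 1.3). All counts and rates below are assumptions, shown as a range.

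**Methods.** Per arm: Clopper-Pearson, as in SAP 2.5.8.3. Difference: SAP 2.5.8.4, with lower limit d − δ and upper limit d + ε, where

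- δ = 1.96 √[l₁(1−l₁)/n₁ + u₂(1−u₂)/n₂]
- ε = 1.96 √[l₂(1−l₂)/n₂ + u₁(1−u₁)/n₁]

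and l, u are the Wilson limits of each arm.

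**Worked example: 22/55 (40%) against 11/55 (20%).**

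- Clopper-Pearson: 27.0–54.1% and 10.4–33.0%. They overlap.
- Wilson limits: 0.2812, 0.5319 and 0.1155, 0.3236.
- δ = 1.96 √[(0.2812 × 0.7188 + 0.3236 × 0.6764)/55] = 0.1715
- ε = 1.96 √[(0.1155 × 0.8845 + 0.5319 × 0.4681)/55] = 0.1566
- Difference 20.0 points, 95% CI 2.9 to 35.7. It excludes zero.

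**Other assumed counts, 55 per arm.**

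| Counts | Separate 95% CIs | Difference (95% CI), points |
|---|---|---|
| 28 v 17 | 37.1–64.6%, 19.1–44.8% (overlap) | 20.0 (1.6 to 36.6) |
| 28 v 16 | 37.1–64.6%, 17.6–42.9% (overlap) | 21.8 (3.5 to 38.2) |
| 11 v 3 | 10.4–33.0%, 1.1–15.1% (overlap) | 14.5 (1.9 to 27.4) |

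For lower-arm rates of about 10% to 50%, the difference interval first excludes zero at an observed gap of about 16 to 20 points. The separate intervals stop overlapping only at about 25 to 29 points.

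**How often each would show a difference.** Exact binomial enumeration over all pairs of counts, 55 per arm:

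| Assumed true rates | Separate CIs do not overlap | Difference CI excludes 0 |
|---|---|---|
| 40% v 20% | 25% | 64% |
| 50% v 30% | 20% | 58% |
| 60% v 40% | 19% | 54% |
| 60% v 30% | 59% | 89% |
| 30% v 30% | 0.3% | 5.1% |

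A standard two-proportion power formula gives 63% for the first row, which agrees. With equal true rates of 20% to 50%, non-overlap occurs 0.3% of the time, against about 4.5% to 5.1% for the difference interval. Comparison by overlap is thus far stricter than the nominal 5%, and it loses most of the sensitivity for gaps of about 20 points.

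**The case against.** The strongest reply is that the analysis matches its objective. Every formal statement of the safety objective is per-group description, and counts, percentages and per-group intervals deliver that. This stands. A reader might infer from Protocol 5.1.2 that comparative safety is the trial's stated objective and that the SAP fails it. The documents do not support that: the comparative wording is confined to the Rationale and Design Justification, so the defect is an inconsistency between those sections and the formal objectives.

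Three further points also stand.

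- A reader might infer that a route comparison of safety is an objective. The comparative wording covers only QIV-HD against QIV-SD. The sentence in Protocol 1.3.2 is text on participant risk, not an estimand.
- A reader might infer that the plan tells people to judge by overlap. It prescribes no such rule. Overlap is a foreseeable habit of readers, and the raw difference can be had by subtracting two tabulated percentages.
- More intervals mean more chances to over-read. Three composites plus ten solicited terms over three contrasts is 39 intervals, and 39 × 0.05 ≈ 2 would be expected to exclude zero with no true differences.

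The appeal to the study being descriptive does not stand, because the same status did not stop the plan from giving immunogenicity its between-group intervals. A labelled risk difference with an interval is description, not testing.

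**Conclusion.** This is a cheap improvement to reporting, not an analysis error. No planned result is wrong or biased, and no data are lost. The plan poses a comparison in Protocol 1.4 and 5.1.2, leaves it out of the formal objectives, and plans no interval for it on any reaction, although SAP 2.5.8.4 already defines a suitable one.

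The size of the gain depends on assumed reaction rates. For true gaps of 20 points, with the lower rate between 20% and 40%, the difference interval excludes zero 54% to 64% of the time, against 19% to 25% for non-overlap of the planned intervals. These figures assume 55 evaluable subjects per arm and a reader who relies on overlap. They say nothing about what the reaction rates will be.

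**What to change.** In SAP 2.4.4, name a short list: any solicited injection site reaction, any solicited systemic reaction and any Grade 3 solicited reaction. Individual solicited terms can be optional. For each, give the risk difference with the 2-sided 95% CI of SAP 2.5.8.4 for:

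- QIV-HD SC minus QIV-SD SC (same route);
- QIV-HD IM minus QIV-HD SC (route only);
- QIV-HD IM minus QIV-SD SC, with a note that it mixes dose, product and route and isolates none of them.

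Use Cohort 2, since Cohort 1 had no QIV-SD arm and its subjects were not randomised concurrently with the control. Label the intervals descriptive and unadjusted for multiplicity. Align the wording of Protocol 1.4 and 5.1.2 with the formal objectives in the Synopsis, Protocol section 2 and SAP 1.2.

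The cost is SAP text and extra table columns, using a method already needed for seroconversion. Design, data collection and sample size are unchanged. The downside is 3 × 3 = 9 more unadjusted intervals, of which 9 × 0.05 = 0.45 would be expected to exclude zero by chance if there were no true differences. Keeping the list short limits this.
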